#### 6.4.1. Immunogenicity Assessments

The protocol mentions two types of immunogenicity assessments:

- Serum nAb level against SARS-CoV-2 as measured by pseudovirus and/or live virus neutralization assays.
- Serum bAb against SARS-CoV-2 spike protein measured by ligand binding assay specific to the SARS-CoV-2 S protein.

In practice, Ab levels are measured using a variety of assays/tests. A complete list of these assays can be found in [Appendix G](#). All summaries of Ab results will be performed by assay/test and participant group, unless otherwise specified.

Unless otherwise specified, summaries of immunogenicity described in this section will display 95% CIs, which are calculated based on the t-distribution of the log-transformed values then back transformed to the original scale for presentation. Similarly, summaries will report the following descriptive statistics will be also provided at each time point: the number of subjects (n), median, minimum, and maximum. Box plots and reverse cumulative distribution curves for each of these reported antibody assay/test results for at all scheduled time points will be presented.

Confidential

#### **6.4.2. Primary Analysis of Neutralizing Antibody Response**

GMC of SARS-CoV-2-specific nAb with corresponding 95% CI will be provided at each time point. The GMC at Day 57 from unvaccinated participants in the 2-dose regimen, the GMC at Day 113 from unvaccinated participants in the 3-dose regimen, Day 29 for SOT participants that are previously vaccinated with Moderna COVID-19 vaccines, and BD-Day 29 for SOT participants that are previously vaccinated with Moderna COVID-19 vaccine/non-Moderna COVID-19 vaccine forms the basis for the evaluation of the primary immunogenicity objective. The GMC at other visits will help address the evaluation of the secondary immunogenicity objective related to nAb levels.

#### **6.4.3. Secondary Analysis of Antibody-Mediated Immunogenicity Response**

For each participant group, the following evaluations will be performed at each time point at which blood samples are collected for immunogenicity, unless otherwise specified.

For each of the reported assay/test results, the following analyses will be performed for both Part A and Part B, unless otherwise specified:

- GM levels of SARS-CoV-2-specific bAb or nAb with corresponding 95% CI will be provided at each time point.
- GMFR of SARS-CoV-2-specific bAb or nAb with corresponding 95% CI will be provided at each post-baseline timepoint over pre-injection baseline at Day 1.

Proportion of subjects with fold-rise  $\geq 2$ , fold-rise  $\geq 3$ , and fold-rise  $\geq 4$  of serum SARS-CoV-2 specific antibody levels from baseline at each post-baseline time points will be summarized with 2-sided 95% Clopper Pearson CIs.

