All nAb and bAb endpoints (Table 1, Study Objectives and Endpoints) will be summarized at each time point with Day 29 (previously vaccinated SOT recipients who receive dose 3), Day 57 (unvaccinated participants who receive 2 doses), Day 113 (unvaccinated SOT participants who receive 3 doses) and BD-29 (participants who receive BD) as the time points of interest. The GM levels and GMFRs of both nAb and bAb will be provided with corresponding 95% CIs.

Reverse cumulative distribution curves for antibody titers for all time points will be presented.

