## 6. Statistical Analysis

### 6.1. General Considerations

The schedule of assessments is provided in Appendix 1 of Protocol Amendment 4.

**Continuous variables** will be summarized using the following descriptive summary statistics: the number of subjects (n), mean, standard deviation (SD), median, minimum (min), and maximum (max).

Confidential

**Categorical variables** will be summarized using counts and percentages.

**Baseline value**, unless otherwise specified, is defined as the most recent non-missing measurement (scheduled or unscheduled) collected before the first dose of IP.

**Pre-booster baseline value** is defined as the most recent non-missing measurement (scheduled or unscheduled) collected before the BD on BD-Day 1.

For the summary statistics of all numerical variables unless otherwise specified, the display precision will follow programming standards. See [Appendix A](#) for variable display standards.

When count data are presented, the percentage will not be displayed when the count is zero in order to draw attention to the non-zero counts. A row denoted “Missing” will be included in count tabulations where specified on the shells to account for dropouts and missing values. The denominator for all percentages will be the number of subjects in the specified group within the analysis set of interest, unless otherwise specified.

**Baseline SARS-CoV-2 status** is determined by using virologic and serologic evidence of SARS-CoV-2 infection on or before Day 1.

Positive SARS-CoV-2 status at Baseline is defined as a positive RT-PCR test for SARS-CoV-2, and/or a positive serology test based on bAb specific to SARS-CoV-2 nucleocapsid (as measured by Roche Elecsys Anti-SARS-CoV-2 assay) on or before Day 1.

Negative status at Baseline is defined as a negative RT-PCR test for SARS-CoV-2 and a negative serology test based on bAb specific to SARS-CoV-2 nucleocapsid (as measured by Roche Elecsys Anti-SARS-CoV-2 assay) on or before Day 1.

**Pre-booster SARS-CoV-2 status**, is determined by using virologic and serologic evidence of SARS-CoV-2 infection prior to the BD in Part B.

Positive pre-booster SARS-CoV-2 status is defined as a positive RT-PCR test for SARS-CoV-2, and/or a positive serology test based on bAb specific to SARS-CoV-2 nucleocapsid (as measured by Roche Elecsys Anti-SARS-CoV-2 assay) on or before the date of BD (BD-Day 1).

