	Booster Phase (Part B)					
	BD-Day 1	BD	≤1, Pre-booster	≤1, Pre-booster	≤1, Pre-booster	≤1, Pre-booster
	1	First	≤1, Pre-dose	≤1, Pre-dose		
Safety Lab	8		[2, 18]	[2, 18]		
	29 (1)	Second	[19, 32]	[19, 32]		
	36		[33, 46]	[33, 46]		
	57 (2)		[47, End of Part A]	[47, 71]		
	85 (3)	Third		[72, 88]	≤1, Pre-dose	
	92			[89, 101]	[2, 18]	
	113 (4)			[102, End of Part A]	[19, End of Part A]	
	Booster Phase (Part B)					
Vital Signs	BD-Day 1	BD	≤1, Pre-booster	≤1, Pre-booster	≤1, Pre-booster	≤1, Pre-booster
	BD-Day 8		[2, 18]	[2, 18]	[2, 18]	[2, 18]
	BD-Day 29		≥19	≥19	≥19	≥19
	1	First	≤1, Pre-dose	≤1, Pre-dose		
	1	First	1, Post-dose	1, Post-dose		
	29 (1)	Second	[2, 29 Pre-dose]	[2, 29 Pre-dose]		
	29 (1)	Second	[29 Post-dose, 43]	[29 Post-dose, 43]		
	57 (2)		[44, End of Part A]	[44, 71]		
Booster Phase (Part B)						

Immunogenicity	BD-Day 1	BD	$\leq 1$ , Pre-booster			
	BD-Day 1	BD	1, Post-booster	1, Post-booster	1, Post-booster	1, Post-booster
	BD-Day 8		[2, 18]	[2, 18]	[2, 18]	[2, 18]
	BD-Day 29		[19, 105]	[19, 105]	[19, 105]	[19, 105]
	BD-Day 181		$\geq 106$	$\geq 106$	$\geq 106$	$\geq 106$
	1	First	$\leq 1$ , Pre-dose	$\leq 1$ , Pre-dose		
	29 (1)	Second	[2, 43]	[2, 43]		
	57 (2)		[44, End of Part A]	[44, 71]		
	85 (3)	Third		[72, 99]	$\leq 1$ , Pre-dose	
	113 (4)			[100, End of Part A]	[2, End of Part A]	
Booster Phase (Part B)						
	BD-Day 1	BD	$\leq 1$ , Pre-booster			
	BD-Day 29		[2, 105]	[2, 105]	[2, 105]	[2, 105]
	BD-Day 181		$\geq 106$	$\geq 106$	$\geq 106$	$\geq 106$

1. Visit day is the target day.
2. Second study injection only applicable to 2-dose unvaccinated with booster and 3-dose unvaccinated participants with booster. Third study injection only applicable to 3-dose unvaccinated participants with booster.
3. SOT recipients who were previously vaccinated with 2 doses of Moderna COVID-19 vaccine will receive dose 3 (first study injection) on Day 1.
4. SOT recipients who were previously vaccinated with mRNA or non-mRNA COVID-19 vaccine primary series (outside of the study) will receive BD (first study injection) on BD-Day 1.
5. Visit window for booster phase (Part B) will be based on booster dose (assessment date – date of BD +1).

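### SAP 6.4.3 measures Part B fold rises from Day 1, so in B2, B3 and B5 they include earlier study doses while in B4 they are already relative to the pre-booster sample

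*SAP*

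**What the plan says.** SAP 6.4.3 opens with its scope: "the following analyses will be performed for both Part A and Part B, unless otherwise specified". It then states that GMFR "will be provided at each post-baseline timepoint over pre-injection baseline at Day 1". No Part B exception follows. The next sentence, on 2-, 3- and 4-fold rises, refers to "specific antibody levels from baseline at each post-baseline time points will be summarized with 2-sided 95% Clopper Pearson CIs".

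SAP 6.1 defines two baselines. The default "is defined as the most recent non-missing measurement (scheduled or unscheduled) collected before the first dose of IP". The pre-booster baseline "is defined as the most recent non-missing measurement (scheduled or unscheduled) collected before the BD on BD-Day 1". The second term is used by name for vital signs in Part B (SAP 6.3.5) and for seroresponse (SAP 6.4.3.1), but not in the GMFR and fold-rise text of 6.4.3.

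Protocol 8.3.3 takes the 2-, 3- and 4-fold rises from Day 1. On fold rises more generally it says only "The GM levels and GMFRs of both nAb and bAb will be provided with corresponding 95% CIs", with no denominator named.

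The notes to the booster part of SAP Table 3 fix what the first study injection is. Previously Moderna-vaccinated recipients (A3, later B3) "will receive dose 3 (first study injection) on Day 1". For recipients who completed a series elsewhere (B4), the note gives the booster itself as the first injection: "outside of the study) will receive BD (first study injection) on BD-Day 1".

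**The concern.** Part B asks what the booster elicits (SAP 2.1). A fold rise answers that only if its denominator is the sample taken just before the booster. With a Day 1 denominator, a B2 or B5 participant who responded to the primary series and still holds that level can count as a 4-fold riser at BD-Day 29 even if the booster added nothing.

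Comparability is also affected. SAP 6.1 reports boosted transplant recipients overall and by primary series (3-dose Moderna, 3-dose Pfizer, other). Participants boosted after an outside series come from B4, where the denominator is the pre-booster sample. B2 and B3, whose series was Moderna, carry a Day 1 denominator. The overall row can mix the two, and the Moderna and Pfizer rows can sit side by side on different scales. If B4 participants with an outside Moderna series are placed in the Moderna row, that row mixes them as well.

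**Working it through.** The plan gives no figure for Part B fold rises. Its one design probability, at least one rejection among 200 transplant recipients at a 3% rate, reproduces (1 - 0.97^200 = 0.998, stated as above 95%) but has no bearing here.

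**Step 1. Denominator by group, reading 6.4.3 literally**

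| Group | First study injection | Denominator at BD-Day 29 and BD-Day 181 | Doses inside the fold rise |
|---|---|---|---|
| B2 | dose 1, Day 1 | before dose 1 | doses 1, 2, 3 and booster |
| B5 | dose 1, Day 1 | before dose 1 | doses 1, 2 and booster |
| B3 | dose 3, Day 1 | before dose 3 | dose 3 and booster |
| B4 | booster, BD-Day 1 | before booster | booster only |

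One label therefore has three meanings: full in-study series plus booster, dose 3 plus booster, and booster alone.

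**Step 2. Exact relation.** For each participant let R = pre-booster level / Day 1 level. Then

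fold rise over Day 1 = fold rise over pre-booster × R,

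and in the same participants

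GMFR over Day 1 = GMFR over pre-booster × GM(R).

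R describes earlier doses and waning, not the booster. In B4, R = 1 by construction.

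**Step 3. Illustration of size.** The documents give neither R nor the SD of the log10 fold rise, so both are assumed. With log-normal fold rises and the same SD under either denominator,

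P(rise ≥ 4) = 1 - Φ[(log10 4 - log10 GMFR) / SD], with log10 4 = 0.602.

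For a booster with no effect:

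| Denominator | GMFR | SD 0.4 | SD 0.6 | SD 0.8 |
|---|---|---|---|---|
| pre-booster | 1 | 6.6% | 15.8% | 22.6% |
| Day 1, R = 5 | 5 | 59.6% | 56.4% | 54.8% |
| Day 1, R = 10 | 10 | 84.0% | 74.6% | 69.1% |

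One cell in full: R = 5, SD 0.4 gives (0.602 - 0.699)/0.4 = -0.242, and 1 - Φ(-0.242) = 0.596.

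For a booster that truly doubles titres, at SD 0.6, the 4-fold rate is 30.8% over pre-booster. Over Day 1 it is 74.6% at R = 5 (GMFR 2 × 5 = 10) and 87.8% at R = 10 (GMFR 2 × 10 = 20).

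**The case against.** **Day 1 could mean BD-Day 1.** For B4 it must, since there is no other Day 1. The protocol sometimes calls the booster day plain Day 1 (the visit list in 3.1; the cellular-immunity note to Table 10), and SAP Table 3 counts booster-phase days from the booster. This reading is possible but less literal. The SAP normally writes BD-Day 1 when it means that day, and it names the pre-booster baseline where it wants it. At best the text is ambiguous.

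**The next subsection already handles it.** SAP 6.4.3.1 reports a 4-fold seroresponse over the pre-booster baseline and analyses participants in both parts on both baselines. This is a real mitigation, and a reader who inferred that the booster's own effect goes unreported would be wrong. But it is limited to a subset of antibodies that is not listed (Table 7 excludes only the multiplex anti-nucleocapsid test), and it gives no GMFR and no 2- or 3-fold rate. GM levels at BD-Day 1 and BD-Day 29 are also reported. Their ratio recovers the booster GMFR if the same participants contribute to both, but not its confidence interval, which needs the within-participant SD.

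**The stakes are low.** This stands. The primary Part B endpoint is a concentration with no baseline (SAP 6.4.2). SAP 3.3 lists no spike-binding or neutralizing GMFR for Part B. The study is for estimation, with no between-group comparisons planned (SAP 4.2).

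**A stronger reading to resist.** A reader might infer that all Part B fold rises credit the booster with the whole primary series. The documents do not support that: it is untrue of B4, and in B3 only dose 3 is carried in.

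**Conclusion.** The point holds for B2, B3 and B5. Taken literally, SAP 6.4.3 gives a cumulative fold rise where a booster fold rise is the natural reading, and B4 sits beside them on a different denominator. For GMFR this is the direct text. For the 2-, 3- and 4-fold rates it follows from the default baseline in SAP 6.1 and from the Day 1 wording in Protocol 8.3.3.

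The multiplication by GM(R) is exact. The contrast of about 55-84% with 7-23% is an illustration that rests on the assumed R, the assumed SD, log-normality and a null booster. It also assumes that R exceeds 1. If levels had waned below the Day 1 value, which is conceivable in B3, the bias would reverse.

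The reach is limited to secondary and exploratory descriptive summaries. The matter is worth correcting before database lock, but it does not threaten the primary Part B result.

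**What to change.** Add to SAP 6.4.3: for BD-Day 29 and BD-Day 181, GMFR and the proportions with at least 2-, 3- and 4-fold rise are relative to the pre-booster baseline defined in 6.1. Any rise over Day 1 at those visits is kept only for B2 and B5, in a separate summary labelled as cumulative over all study doses, and is not pooled with B3 or B4.

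Record the departure from the protocol's Day 1 wording in SAP Section 7, which now says that no changes apply. Protocol Section 8 allows changes to other secondary or exploratory analyses to be listed in the SAP.

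The cost is one or two sentences, an entry in Section 7 and a change of denominator in the programs. No sample is added, because immunogenicity blood before the booster is already scheduled for every Part B participant (Protocol Table 10). Sample size is unchanged, and so are the B4 results.

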##### **6.4.3.1. Seroresponse Rate (SRR) of the Primary Series and Booster**

For a subset of the antibodies of interest, seroresponse rate, defined as number of subjects achieving seroresponse, will be summarized at each post-baseline timepoint. There will be 2 baseline definitions used for determining seroresponse rate: 1) Pre-vaccination baseline is defined as the sample collected prior to any injection in Part A (primary series) and 2) Pre-booster baseline is defined as the sample collected prior to BD in Part B. Subjects that are enrolled in both Part A and Part B will be analyzed based on both types of baseline (pre-vaccination and pre-booster).

If missing pre-vaccination baseline (no available serum samples), and the subject did not have SARS-CoV-2 infection prior to vaccination (i.e. negative SARS-CoV-2 status at pre-vaccination of primary series), the subject's pre-vaccination baseline antibodies will be Confidential

assumed to be < LLOQ. Similarly, for SOT recipients who completed primary series vaccination with an mRNA or non-mRNA COVID-19 vaccine outside of the study, if pre-booster baseline antibodies are missing and the subject did not have SARS-CoV-2 infection prior to receiving BD (i.e. negative SARS-CoV-2 status), the subject's pre-booster baseline antibodies will be assumed to be < LLOQ.

- Two definitions for seroresponse will be used for analyses: 1) 4-fold rise seroresponse based on pre-vaccination baseline and 2) 4-fold rise seroresponse based on pre-booster baseline. Seroresponse based on pre-vaccination baseline is defined in 2 ways:
  - 4-fold rise seroresponse (primary approach), measured by an increase of SARS-CoV-2 specific bAb or nAb from pre-vaccination baseline < LLOQ to at least  $4 \times$  LLOQ, or a 4-fold or greater rise if pre-vaccination baseline  $\geq$  LLOQ.
  - If assay-specific critical fold rise becomes available, seroresponse based on assay-specific critical threshold may be provided.
- The 4-fold rise definition will be used for seroresponse analyses at each post-baseline for all subjects in Part A (regardless of whether subjects continue to Part B) and all subjects in Part B.
- Seroresponse based on pre-booster baseline follows the same definition as pre-vaccination seroresponse.
- Difference in seroresponse rates between the BD and the primary series and among participant groups may be provided with 2-sided 95% CIs using the Miettinen-Nurminen's method.

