#### **5.3.1. Modified Intent-to-Treat Set (Part B)**

The mITT Set (Part B) consists of all participants in the Safety Set who received BD and had no immunologic or virologic evidence of prior COVID-19 (ie, negative RT-PCR test and bAb against SARS-CoV-2 nucleocapsid (as measured by Roche Elecsys Anti-SARS-CoV-2 assay)) below LOD or LLOQ at pre-booster before the BD.

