#### **5.3.3. Per-Protocol Immunogenicity Set (Part B)**

PP Immunogenicity Set (Part B) includes all participants in the mITT Set (Part B) who received planned BD per schedule, and SOT recipients who completed primary series vaccination with an mRNA or non-mRNA COVID-19 vaccine outside of the study that are in the mITT Set (Part B). The participants who complied with the timings of immunogenicity blood sampling to have post-booster results available for at least one assay component corresponding to the immunogenicity analysis objective, and participant had no major protocol deviations that impact immune response during the period corresponding to the immunogenicity analysis objective will be included.

The PP Immunogenicity Set (Part B) will serve as the primary analysis population for the analysis of SARS CoV 2-specific bAb and nAb immunogenicity data in Part B.

Confidential

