Negative pre-booster SARS-CoV-2 status is defined as no virologic or serologic evidence of SARS-CoV-2 infection on or before BD-Day 1 (pre-booster), i.e. RT-PCR result is not positive if available at BD-Day 1 and a negative bAb specific to SARS-CoV-2

Confidential

nucleocapsid (as measured by Roche Elecsys Anti-SARS-CoV-2 assay) on or before BD-Day 1.

**Study day relative to the first study injection** will be calculated as below:

- a) Study day prior to the first study injection will be calculated as: date of assessment/event – date of the first study injection;
- b) Study day on or after the date of the first study injection will be calculated as: date of assessment/event – date of the first study injection + 1.

**Study day relative to the most recent study injection** will be calculated as below:

- a) Study day prior to the first study injection will be calculated as: date of assessment/event – date of the first study injection;
- b) Study day on or after the date of the first study injection but before the second study injection (if applicable) will be calculated as: date of assessment/event – date of the first study injection + 1;
- c) Study day on or after the date of the second study injection but before the third study injection (if applicable) will be calculated as: date of assessment/event – date of the second study injection + 1;
- d) Study day on or after the date of the second study injection will be calculated as: date of assessment/event – date of the second study injection + 1 provided that if study day is on the same day as the second study injection, the time is after the second study injection time;
- e) Study day on or after the date of the third study injection but before the BD (if applicable) will be calculated as: date of assessment/event – date of the third study injection + 1;
- f) Study day on or after the date of the third study injection will be calculated as: date of assessment/event – date of the third study injection + 1 provided that if study day is on the same day as the third study injection, the time is after the third study injection time;
- g) Study day on or after the date of the BD will be calculated as: date of assessment/event – date of the BD + 1 provided that if study day is on the same day as the BD, the time is after the BD time.

Confidential

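### SAP 6.4.3.1 sets a missing pre-booster antibody value below LLOQ in already vaccinated Group B4 on evidence that excludes only infection; minor, but any misclassification raises the seroresponse rate

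*SAP*

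**What the plan says.** SAP 6.4.3.1 scores seroresponse as reaching at least 4 x LLOQ when the baseline is below LLOQ, and as a rise of at least 4-fold when the baseline is at or above LLOQ. The same definition serves the pre-vaccination and the pre-booster baseline.

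The section first covers a missing pre-vaccination baseline, then extends the idea to transplant recipients whose primary series was completed outside the study. The trigger is "if pre-booster baseline antibodies are missing and the subject did not have SARS-CoV-2 infection prior to receiving BD", and the consequence is that "pre-booster baseline antibodies will be assumed to be < LLOQ".

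SAP 6.1 defines negative pre-booster status through the clause "RT-PCR result is not positive if available at BD-Day 1 and a negative bAb specific to SARS-CoV-2" nucleocapsid. SAP 6.1 also sets the general default that missing antibody results are not imputed unless stated otherwise, so 6.4.3.1 is a deliberate exception. No pre-booster imputation is stated for Groups B2, B3 or B5. On comparisons, 6.4.3.1 adds: "Difference in seroresponse rates between the BD and the primary series and among participant groups may be provided".

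**The concern.** A below-LLOQ default is sensible for someone who has been neither vaccinated nor infected. Group B4 is defined by having been vaccinated: Protocol 4.2.1 requires a completed primary series at least 4 months before the booster. Protocol 3.1 calls nucleocapsid a nonvaccine antigen whose antibody signifies infection, and Protocol 1.2 says that mRNA-1273 encodes spike. A negative nucleocapsid test therefore says nothing about the spike-binding and neutralizing antibody on which seroresponse is scored (SAP Table 7 excludes nucleocapsid from seroresponse).

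At stake is a descriptive rate for one group, with an error that can go only in the favourable direction. It could also pass into the optional differences among groups, since the other boosted groups have no matching rule.

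**Working it through.** The plan states no seroresponse figure, so there is none to reproduce. The check has three parts.

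**1. Direction.** Let L be the LLOQ, B the true pre-booster level and Y the post-booster level.

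- Rule with the true baseline: responder if Y >= 4 x max(B, L).
- Rule with the imputed baseline: responder if Y >= 4 x L.

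Because 4 x max(B, L) >= 4 x L, every true responder is also a responder under the imputation. The two rules disagree only when B > L and 4L <= Y < 4B. For example, with L = 1, B = 5 and Y = 10, the rise is 2-fold (not a response), but 10 >= 4 scores a response. On a 400 x 400 grid of (B, Y), 26,733 of 160,000 points moved up to responder and 0 moved down.

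**2. Reach.**

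- The Part B Per-Protocol Immunogenicity Set is drawn from the Part B mITT Set (SAP 5.3.3), which requires nucleocapsid antibody "below LOD or LLOQ at pre-booster before the BD" (SAP 5.3.1).
- Protocol Table 10 lists the spike, neutralizing and nucleocapsid samples as one pre-dose BD-D1 collection.
- In that set, therefore, the rule normally acts only when the nucleocapsid test gave a result and the pseudovirus neutralization or multiplex binding assay (SAP Table 7) did not.

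**3. Size.** The documents do not give the share of B4 baselines that will be missing, B4's pre-booster levels, or the fold rise in transplant recipients. One ceiling needs no distribution: with 50 participants (the minimum in SAP 4.1), each imputed participant moves the rate by at most 1/50 = 2 points.

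For scenario values, the assumptions were:

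- 30%, 50% or 70% have pre-booster antibody, with log10 mean 0.5, 1.0 or 1.5 above LLOQ and SD 0.6;
- the rest sit at 0.5 x LLOQ, the SAP 6.1 substitution;
- the log10 rise has SD 0.4 or 0.6.

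Protocol 3.2 cites detectable antibody in 30-60% of transplant recipients after 2 doses. That is context for the assumed share, not a measure of it. The gap is the imputed rate minus the true rate among imputed participants, from 2,000,000 draws per scenario. Multiplying it by 100/50 = 2 gives points per imputed participant at n = 50.

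| Mean rise | Gap, SD 0.4 | Points at n = 50 | Gap, SD 0.6 | Points at n = 50 |
|---|---|---|---|---|
| 2-fold | 0.123-0.509 | 0.25-1.02 | 0.094-0.430 | 0.19-0.86 |
| 4-fold | 0.092-0.337 | 0.18-0.67 | 0.078-0.324 | 0.16-0.65 |
| 8-fold | 0.045-0.155 | 0.09-0.31 | 0.053-0.205 | 0.11-0.41 |
| 16-fold | 0.014-0.046 | 0.03-0.09 | 0.029-0.106 | 0.06-0.21 |
| 37-fold | 0.0017-0.0055 | 0.003-0.011 | 0.010-0.037 | 0.02-0.07 |
| 83-fold | 0.0001-0.0003 | below 0.001 | 0.003-0.010 | 0.006-0.02 |

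False non-responders were 0 in every scenario. The 37- and 83-fold rows use the Omicron neutralizing rises that Protocol 1.2.2 reports after 50 µg and 100 µg boosters in another study. They are not transplant-specific.

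**The case against.** The best defence is that the rule will hardly ever act. The preceding sentence, on the pre-vaccination baseline, explains missing as having no available serum, and the B4 sentence follows it with a linking word. If that explanation carries over, a B4 participant without BD-D1 serum would normally have no nucleocapsid result either. Such a participant has no negative status and no place in the Per-Protocol Immunogenicity Set, which leaves the rule nearly inert. This is a fair reading, but the B4 sentence does not repeat the explanation, so the text also covers a failed assay beside a valid nucleocapsid result. The objection limits the size; it does not make the inference right.

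The size figures are also assumed. At the one 100 µg booster rise in the documents (83-fold), the gap is 1 point or less even among imputed participants. That stands.

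A reader might infer that the same error affects Group A3, since "Pre-vaccination baseline is defined as the sample collected prior to any injection in Part A (primary series") and, for that group, "SOT recipients who were previously vaccinated with 2 doses of Moderna COVID-19 vaccine will receive dose 3 (first study injection) on Day 1". The documents do not support calling this an error. The pre-vaccination sentence is limited to absent serum, which would normally remove the nucleocapsid result too. Its status condition also refers to the time before the primary series; if that means before the outside doses, below LLOQ is reasonable in an uninfected person. It is an ambiguity to clarify.

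**Conclusion.** The rule is wrong as written, and the point is minor. Negative SARS-CoV-2 status does not justify a below-LLOQ pre-booster baseline in people who have completed a vaccine series, and misclassification can only raise B4's pre-booster seroresponse rate. That direction follows from the definitions alone and needs no assumption.

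The size does need assumptions. At n = 50 it runs from near zero at large fold rises to about 1 point per imputed participant at a 2-fold rise, and the number imputed is unknown but probably small. These are scenario values, not bounds. The weight of one participant is larger in the split by primary series in SAP 6.1.

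A reader might infer that the Part B immunogenicity conclusion is inflated. The documents do not support that. The primary result is the neutralizing geometric mean at BD-Day 29 (SAP 6.4.2), which uses no baseline; seroresponse is not among the endpoints in SAP 3.1 to 3.3; and differences in seroresponse are optional.

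**What to change.** Delete the below-LLOQ assumption for the Group B4 pre-booster baseline and let the SAP 6.1 default apply. Suggested wording for 6.4.3.1:

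- The main pre-booster seroresponse rate uses participants with both a pre-booster and a post-booster result. The number with a missing pre-booster result is reported.
- As a sensitivity analysis, bounds are given over all participants with a post-booster result. A missing baseline with a post-booster value below 4 x LLOQ is a non-responder in both bounds. A missing baseline with a post-booster value of at least 4 x LLOQ is a non-responder in the lower bound and a responder in the upper bound.

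The upper bound reproduces the current rule. For example, take 29 responders among 48 with both results, plus 2 missing baselines whose post-booster values are at least 4 x LLOQ. The main rate is 29/48 = 60.4%, and the bounds are 29/50 = 58.0% and 31/50 = 62.0%; the current rule gives 62.0%. If both post-booster values were below 4 x LLOQ, both bounds would be 58.0% and the main rate would lie above them, because its denominator differs. The main rate is unbiased only if missingness is unrelated to response, so all three should be shown together.

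Do not report a single rate that drops only the undetermined participants, because it selects on outcome. At n = 50 with one missing baseline, an 8-fold rise and SD 0.4, its bias is -0.21 to -0.44 point against +0.09 to +0.31 for the current rule, and it is larger in size in 7 of 9 scenarios.

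Also add a clarification that the pre-vaccination below-LLOQ rule refers to a baseline before any COVID-19 vaccination.

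The cost is a wording change and two extra table rows. A few participants may leave the main denominator, and B4's rate may look slightly less favourable.
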